2.3 Primary Endpoints

2.3.1 The primary endpoint of the study is feasibility of RC after ICI + PULSAR, defined as the proportion of enrolled patients who complete three courses of PULSAR followed by radical cystectomy while remaining on ICI therapy, within sixteen weeks of initiation of PULSAR. It is anticipated that reasons for protocol non-completion may include progression to nonresectable disease and patient intolerance of treatment.

2.4 Secondary Endpoints

2.4.1 Progression free survival (PFS): Primary disease progression will be defined as any of the following. Progression-free survival will be measured from the date of the first PULSAR treatment.

1. Emergence of new sites of disease or locoregionally recurrent disease as defined by RECIST 1.1 criteria.

2. Pathologic demonstration of recurrent or metastatic disease (e.g. core needle biopsy, fine needle aspirate, diagnostic peritoneal biopsy).
3. Initiation of a patient on palliative or salvage treatment due to clinical concern for disease progression.
4. For patients with intraoperative concern for grossly incomplete disease resection (R2), the date of the first postoperative imaging study showing disease progression by RECIST 1.1 criteria (i.e., 20% increase in the sum of the diameters of all lesions, with an absolute increase of at least 5 mm; or the appearance of any new lesion).

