Statistical Methodology	Proportion of patients completing the study will be calculated and the trial will be deemed successful if the number of patients completing the protocol exceeds the futility threshold of 60%. Progression-free survival, the secondary endpoint, will be estimated by the Kaplan-Meier method and compared with historic controls using the log-rank test.

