1.0 BACKGROUND AND RATIONALE

1.1 Disease Background

Muscle invasive bladder cancer (MIBC) has high metastatic potential and warrants aggressive treatment. Standard-of-care treatment in MIBC involves platinum-based neoadjuvant chemotherapy (NACT) followed by radical cystectomy (RC) with pelvic lymph node dissection (PLND) and urinary diversion¹⁻³. Bladder-conserving chemoradiation therapy is an appropriate alternative in select patients, though it is used in only a minority of cases in the United States⁴. Bladder cancer carries significant morbidity and mortality and has been cited as the most expensive malignancy to manage, on a per-patient basis, in the United States^{5,6}.

Metastatic spread to regional lymph nodes is an adverse prognostic factor in bladder cancer. In several large case series reported without use of neoadjuvant chemotherapy, patients with pathologically positive lymph nodes (pN+) at radical cystectomy had 5-year overall or disease-specific survival rates of only 22-30%⁷⁻¹⁰. The addition of neoadjuvant chemotherapy (NACT) or downstaging chemotherapy (DCT) in patients with clinically positive lymph nodes (cN+) improves outcomes, particularly in those who achieve a pathologic complete response to DCT^{11,12}. However, patients who fail to respond to downstaging or neoadjuvant chemotherapy have an especially poor prognosis, with a 5-year overall survival rate of only 16% in one recent series¹³. It should also be noted that a significant proportion (up to 25-50%) of patients with bladder cancer are ineligible for chemotherapy due to medical comorbidities¹⁴.

We recently reviewed the outcomes of patients undergoing radical cystectomy at UT Southwestern with bulky cN+ bladder cancer¹⁵. Among the subset of patients who did not receive or failed to respond to DCT, the 2-year progression-free survival was only 30%, despite aggressive salvage treatment. Importantly, a majority of patients (84%) in the study received downstaging chemotherapy and all were medically eligible for chemotherapy. This suggests that chemo-ineligible patients presenting with cN+ disease were not offered curative treatment. Direct comparisons with historic literature are difficult, due to widely varying definitions of cN+ disease; however, the progression-free survival of our bulky cN+ cohort closely parallels that of the cN2-3 and cM1a cohorts within one large published series¹¹, confirming that our bulky cN+ cohort represents an especially high-risk population.

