2.2 Secondary Objectives

2.2.1 To determine the 2-year progression-free survival (PFS) in patients with cN+ bladder cancer in all enrolled patients, and in the subset of patients completing the full protocol of ICI + PULSAR + RC.

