9.0 STATISTICAL CONSIDERATIONS

9.1 Study Design/Study Endpoints

This is a single institution, single arm, phase II trial. We hypothesize that the combination of standard-of-care ICI with PULSAR will be feasible and does not result in delays in treatment. We define a target rate of protocol completion (completion of radical cystectomy within sixteen weeks of initiation of PULSAR) of 90%, with a lower boundary of futility at 60%.

The secondary endpoint is efficacy, defined by 2-year recurrence-free survival.

As discussed above, we additionally plan to assess safety (defined by the 90-day rate of Clavien-Dindo Grade \geq III complications following radical cystectomy); pathologic outcomes; rates of residual disease at surgery; and ureteroenteric anastomotic stricture rate.

If the incidence of Grade 3 or higher treatment-related adverse events convincingly exceeds 50%, a threshold we are comfortable with given the potential benefit of the regimen as well as our experience in managing the side effects in this patient population, we will temporarily halt the study and carefully review the available data at that point in order to suggest a potential modification. If we determine that high rates of adverse events are intrinsically related to protocol and no modification will reasonably decrease this rate to an acceptable threshold (below 50%), then we will terminate the study.

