9.3 Data Analyses

The primary endpoint, protocol completion, will be assessed by calculating the proportion of patients completing radical cystectomy within sixteen weeks of initiating PULSAR treatment. If the proportion of patients undergoing cystectomy exceeds 60%, the null hypothesis (that use of ICI+PULSAR+RC is not feasible) will be deemed to have been rejected.

For the secondary endpoint, progression-free survival will be determined as described above, and will be reported by means of Kaplan-Meier survival curves, median progression-free survival time, and proportion of patients without progression at two years. Comparison will be made to the trial-eligible subset of patients in a historic control series using the log-rank test. The 2-year progression-free survival rate in the historic cohort was 30%. The null hypothesis will be rejected if the one-sided *p* value for the comparison is less than 0.10.

Additional planned analyses include the following, all of which will be reported with simple descriptive statistics (*n* / *N* and percentage):

Major complication rate: A major surgical complication will be defined as any postoperative complication of Clavien-Dindo Grade III or higher.

Pathologic outcomes: Pathologic outcomes will be defined as follows, based on the final surgical pathology report:

1. Pathologic complete response: no viable disease remaining in the specimen (ypT0 N0).
2. Pathologic non-muscle-invasive downstaging: primary tumor without muscle invasion, and no viable disease in lymph nodes (\leq ypT1 N0).
3. Pathologic organ-confined downstaging: primary tumor confined to detrusor muscle, and no viable disease in lymph nodes (\leq ypT2 N0).
4. Nodal complete response: no viable disease in lymph nodes, regardless of primary tumor stage (ypTany N0).

Residual disease: Residual disease at surgery will be defined as follows:

1. Microscopic residual disease (R1) will be defined as any positive soft tissue margin on the final surgical pathology report, excluding carcinoma *in situ* at ureteral margins.
2. Gross residual disease (R2) will be defined as any grossly positive tissue margin reported on a pathology report, *or* the operating surgeon's subjective report of grossly unresectable disease including bulky matted lymph nodes.

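### The historic PFS comparison in 9.3 has no common time zero and does not name the trial population tested, so the p<0.10 rule is not interpretable as written

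*Combined protocol and SAP*

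**What the plan says.** - **Trial clock.** Section 2.4.1: "Progression-free survival will be measured from the date of the first PULSAR treatment". Section 6.1.6 repeats this.
- **Comparison.** Section 9.3: "Comparison will be made to the trial-eligible subset of patients in a historic control series using the log-rank test". The null is rejected at one-sided p below 0.10. The study summary also says PFS will be "compared with historic controls using the log-rank test".
- **Comparator.** Section 1.1 introduces the series with "We recently reviewed the outcomes of patients undergoing radical cystectomy at UT Southwestern with bulky cN"-positive disease. It adds that 84% received downstaging chemotherapy and that "all were medically eligible for chemotherapy". The 30% two-year rate belongs to the subset who did not receive, or did not respond to, that chemotherapy. No time origin or patient count is given.
- **Populations.** Section 2.2.1 asks for two-year PFS "in all enrolled patients, and in the subset of patients completing the full protocol of ICI + PULSAR + RC". Section 9.3 has one test and names neither population.
- **Non-completion.** Section 2.3.1 expects that "reasons for protocol non-completion may include progression to nonresectable disease and patient intolerance of treatment".
- **Endpoint name.** Section 9.1: "The secondary endpoint is efficacy, defined by 2-year recurrence-free survival". Section 9.2 also calls the historic 30% recurrence-free survival, while 1.1 and 9.3 call it progression-free survival.

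**The concern.** A log-rank test compares two groups from the same starting point. Here one group starts at first PULSAR, and the other consists of people who never had PULSAR and were all operated on. The two readings of 9.3 go wrong in different ways.

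- **Completers tested.** A completer has by definition reached surgery. Section 1.4 sends patients with new distant metastases to non-curative management, and 6.1.2 makes pelvic nodes non-evaluable at the scan before cystectomy. The interval from PULSAR to surgery is therefore largely event-free by selection. If the historic clock starts at surgery, only the trial curve gets that extra time.
- **All enrolled tested.** Patients who progress and never reach surgery count in the trial curve. The historic series excludes such patients by construction.

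This is the only formal efficacy test in the plan. Crossing or missing p=0.10 could come from the choice of clock or population and not from the regimen, and either choice could be made after the data are seen.

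**Working it through.** **1. The plan's power figure.** Section 9.2 gives 24 patients, 30% against 57% at two years, one-sided alpha 0.10 and 90% power. An exact binomial test against a fixed 30%, rejecting at 11 or more of 24, has size 0.074 and power 0.904, so 90% is reproduced as a one-sample figure. As a two-sample log-rank test over 24 months (hazard ratio ln 0.57 / ln 0.30 = 0.467), simulated power is 76%, 83% and 88% for a historic N of 24, 50 and 100. That range of N is an assumption.

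**2. First PULSAR to surgery.** Section 4.1 has two intervals of 12-16 days, so fraction 3 falls on day 24-32. Adding 4-8 weeks (28-56 days) gives day 52-88. The 16-week limit in 2.3.1 is day 112. In months: 1.71, 2.89 and 3.68.

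**3. Completers, no true effect, historic clock at surgery (assumption).** Constant hazard h = -ln(0.30)/24 = 0.0502 per month. With gap L and no events before surgery, two-year PFS from PULSAR is exp(-h(24-L)). With half the hazard before surgery it is exp(-h(24-L/2)). False-positive rates are for a simulated two-sample log-rank test with 22-24 completers and historic N 24-100. With no gap the same test gives 9-10%.

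| Surgery at | Apparent 2-year PFS, no earlier events | False-positive rate | Apparent 2-year PFS, half hazard before surgery | False-positive rate |
|---|---|---|---|---|
| Day 52 | 32.7% | 17-18% | 31.3% | about 13% |
| Day 88 | 34.7% | 24-27% | 32.3% | about 16% |
| Day 112 | 36.1% | 29-33% | 32.9% | about 18% |

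**4. Earlier historic clock.** With 22 completers, surgery at day 52-88 and no events before surgery, the false-positive rate is 12-18% if the historic clock starts 35 days before surgery, 7-13% at 70 days and 2-4% at 140 days.

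**5. All 27 enrolled, historic clock at surgery.** Suppose a share q progresses before planned surgery (assumed 10%, 25% or 40%). With no effect, two-year PFS is (1-q)exp(-h(24-L)). If those operated have the planned effect, h is replaced by -ln(0.57)/24 = 0.0234. Power is for a one-sample log-rank test against 30%; with no gap and no losses it is 95%. Ranges cover day 52 to day 88.

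| q | 2-year PFS, no effect | 2-year PFS, planned effect | Power |
|---|---|---|---|
| 10% | 29.4-31.2% | 53-55% | 85-90% |
| 25% | 24.5-26.0% | 45-46% | 42-49% |
| 40% | 19.6-20.8% | 36-37% | 8-11% |

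At 10% the event-free lead of the operated patients roughly offsets the early progressions (false-positive rate 7-13%). At higher shares the comparison runs clearly against the trial.

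**6. Test with one clock.** Section 4.11 follows patients for two years from first PULSAR, which leaves 24 - 3.68 = 20.3 months after surgery at the 16-week limit. A 20-month horizon therefore needs no added follow-up. Rates at 20 months are 0.30^(20/24) = 36.7% and 0.57^(20/24) = 62.6%. The 90% target and 60% futility bound give 0.90 x 27 = 24.3 and 0.60 x 27 = 16.2 completers. Simulated size is 9-10%. Power for historic N 24-100 is 72-85% with 24 completers and 64-74% with 16.

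**The case against.** - **The historic clock may start earlier, or the cited paper may define it.** This stands as to direction. A reader might infer from the table in step 3 that the plan favours the regimen. The documents do not support that, because step 4 shows the bias shrinking and reversing. The plan must still state the origin, and a first-PULSAR clock cannot apply to the historic patients.
- **The inflation in step 3 is an upper bound.** This stands. Section 5.5.4 lets the investigator continue treatment after progression, and 2.4.1 also counts pathologically shown disease, so a completer can have an event before surgery. The half-hazard columns show the effect of allowing for this.
- **The comparator is already restricted to trial-eligible patients, and 1.1 discloses their chemotherapy eligibility.** This is true, but neither supplies a time origin or a tested population. It would also go too far to say that Cohort 1 has no counterpart. That holds for patients medically unfit for any platinum. Those who refused chemotherapy, or who are unfit only for cisplatin, may have one.
- **It is a secondary endpoint.** This is true. The trial's success criterion is protocol completion, which is unaffected, and 9.3 reports Kaplan-Meier results whatever the p-value.
- **Testing completers from surgery conditions on an outcome after enrolment and shortens the horizon.** This is a real cost. It follows from choosing an operated-only comparator.

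Two other inferences should be avoided. The historic patients were not treated by cystectomy alone, since 84% of the series received downstaging chemotherapy. The stated 90% power is not a wrong calculation for a fixed 30% benchmark; it does not describe a two-sample log-rank test with a historic group of 24-100.

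**Conclusion.** The concern holds and should be corrected before analysis. That the trial and historic clocks differ, that the historic origin and size are missing, and that the tested population is unnamed all follow from the text without assumption.

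The size does rest on assumptions: constant hazard, 30% at two years, historic N 24-100 and a historic clock at surgery. Under these, testing completers gives at most 17-33% false positives against a nominal 10%, or about 13-18% with half the hazard before surgery. The documents do not fix the direction. An earlier historic clock can take the rate below 10%, and including unoperated patients pulls against the trial. The supported conclusion is that the result of the p<0.10 rule depends on choices the plan has not made, and not that the plan is biased in favour of the regimen. Confidence in the magnitude is medium.

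**What to change.** In 9.3:

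- State the historic series' time zero, number of patients and endpoint definition.
- Use the same time origin in both series for any formal log-rank test. Because the comparator is operated-only, test the full-protocol completers of 2.2.1, timed from cystectomy in both series and truncated at 20 months. Note in 2.4.1 and 6.1.6 that this clock applies only to the historic comparison.
- Report all-enrolled two-year PFS from first PULSAR as a Kaplan-Meier estimate with a 95% confidence interval, described as not directly comparable with the series.
- State that the test is conditional on reaching surgery and that selection differences remain, including that every historic patient was medically eligible for chemotherapy.
- If the historic records cannot be re-timed, call the comparison descriptive and drop the p<0.10 rule.

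Use PFS as the single term in 9.1 and 9.2, and align the study summary with the revised comparison. In 9.2, restate the power: about 72-85% with 24 completers or 64-74% with 16, against 76-88% by the same two-sample method with 24 patients at 24 months.

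The cost is wording changes and re-timing of the institution's own records, with no added follow-up. The downsides are a conditional inference, a horizon shorter than two years, pre-surgical progressions of patients who never reach surgery appearing only in the all-enrolled estimate, and somewhat lower power.

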6.0 MEASUREMENT OF EFFECT

6.1 Antitumor Effect

Response and progression following radical cystectomy (as distinct from criteria for trial eligibility, which are defined in section 3.1.2 above), will be evaluated in this study using the new international criteria proposed by the Response Evaluation Criteria in Solid Tumors (RECIST v 1.1) Committee [Eur J Cancer. 2009;45(2):228-247]. Changes in only the largest diameter (unidimensional measurement) of the tumor lesions are used in the RECIST v1.1 criteria.

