6.1.2 Disease Parameters

Measurable Disease: Tumor lesions: Must be accurately measured in at least one dimension (longest diameter in the plane of measurement is to be recorded) with a minimum size of:

1. 10 mm by CT scan (CT scan slice thickness no greater than 5 mm)
2. 10 mm caliper measurement by clinical exam (lesions which cannot be accurately measured with calipers should be recorded as non-measurable)
3. 20 mm by chest x-ray.

Malignant lymph nodes: To be considered pathologically enlarged and measurable, a lymph node must be ≥ 15 mm in short axis when assessed by CT scan (CT scan slice thickness recommended to be no greater than 5 mm).

Lymph nodes merit special mention since they are normal anatomical structures which may be visible by imaging even if not involved by tumor. Pathological nodes which are defined as measurable and may be identified as target lesions must meet the criterion of a short axis of ≥ 15 mm by CT scan. Only the short axis of these nodes will contribute to the baseline sum. The short axis of the node is the diameter normally used by radiologists to judge if a node is involved by solid tumor. Nodal size is normally reported as two dimensions in the plane in which the image is obtained (for CT scan this is almost always the axial plane; for MRI the plane of acquisition may be axial, sagittal or coronal). The smaller of these measures is the short axis. For example, an abdominal node which is reported as being 20 mm x 30 mm has a short axis of 20 mm and qualifies as a malignant, measurable node. In this example, 20 mm should be recorded as the node measurement. All other pathological nodes (those with short axis ≥ 10 mm but < 15 mm) should be considered non-target lesions. Nodes that have a short axis < 10 mm are considered non-pathological and should not be recorded or followed.

Note: Previously irradiated lesions are non-measurable except in cases of documented progression of the lesion since the completion of radiation therapy. For this reason, and because of the potential for pseudoprogression as discussed above, the pelvic lymph nodes will not be considered evaluable at the initial restaging scan following PULSAR and prior to radical cystectomy.

Non-measurable disease.

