6.1.6 Progression-Free Survival

Progression-free survival (PFS) is defined as the duration of time from start of PULSAR treatment to time of progression. Progression is defined as any of:

1. Radiologic disease progression, as defined by RECIST 1.1 criteria above.
2. Pathologic demonstration of recurrent or metastatic disease (e.g. core needle biopsy, fine needle aspirate, diagnostic peritoneal lavage).
3. Initiation of a patient on salvage or palliative treatment due to clinical concern for disease progression.
4. For patients with documented concern (by the operating surgeon) for grossly incomplete disease resection (R2) including bulky unresectable lymph nodes, the date of the first postoperative imaging study showing disease progression by RECIST 1.1 criteria.

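### The two PFS definitions disagree on whether growth of existing, never-resected disease is an event, and the analysis section does not say which one governs

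*Combined protocol and SAP*

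**What the plan says.** Objective 2.2.1 asks for 2-year PFS "in all enrolled patients, and in the subset of patients completing the full protocol of ICI + PULSAR + RC". Patients who never reach surgery are therefore in the first of these populations.

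Section 2.4.1 lists four events:

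1. "Emergence of new sites of disease or locoregionally recurrent disease as defined by RECIST 1.1 criteria".
2. Pathologic proof of recurrent or metastatic disease.
3. A change of management, namely the start of salvage or palliative therapy because progression is suspected clinically.
4. A rule for operated patients only: "For patients with intraoperative concern for grossly incomplete disease resection (R2), the date of the first postoperative imaging study showing disease progression". Growth is judged under RECIST 1.1, and this is the only item of 2.4.1 that states the rule of 20% and 5 mm growth.

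Section 6.1.6 gives a second list. Items 2 to 4 are close to those above, but item 1 is "Radiologic disease progression, as defined by RECIST 1.1 criteria above". The criteria it points back to, in 6.1.4.1 and 6.1.4.2, count growth of target lesions over the nadir and unequivocal progression of existing non-target lesions.

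Two further statements bear on 6.1.6. Section 6.1 introduces the RECIST rules for "Response and progression following radical cystectomy". Section 6.1.2 makes irradiated lesions non-measurable unless they have progressed since radiation, and adds that "the pelvic lymph nodes will not be considered evaluable at the initial restaging scan following PULSAR and prior to radical cystectomy".

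Section 9.3 refers only to the description given above, without naming either section, and compares PFS with a historic 2-year rate of 30% at a one-sided 0.10 level.

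**The concern.** Section 2.3.1 itself expects some patients to miss surgery because their disease becomes nonresectable. In such a patient, growth of the tumour already present is one way the disease can progress. That is the situation in which the two lists differ.

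The estimate in all enrolled patients, and the formal comparison with 30%, can then depend on which section the analyst follows. The choice is not neutral, because 2.4.1 has the narrower first item and so can only leave more patients event-free. If it is made after the data are seen, the result is open to challenge whichever way it falls.

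**Working it through.** **Step 1. The lists side by side, for a patient without cystectomy.**

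| Finding | 2.4.1 | 6.1.6 |
|---|---|---|
| New lesion | event (item 1) | event (item 1) |
| Pathologic proof of recurrent or metastatic disease | event (item 2) | event (item 2) |
| Start of palliative or salvage treatment for suspected progression | event (item 3) | event (item 3) |
| Growth of the bladder tumour only | not named | event (item 1 with 6.1.4), if 6.1 reaches these patients |
| Growth of pelvic nodes only, initial post-PULSAR scan before surgery | not named | not evaluable (6.1.2) |
| Growth of pelvic nodes only, later scan | not named | event (item 1 with 6.1.4), if 6.1 reaches these patients |

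The lists differ in rows 4 and 6.

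**Step 2. Does 6.1.6 reach unresected patients?** The scope sentence of 6.1 suggests that it may not. The node exemption in 6.1.2 suggests that it does, since exempting pelvic nodes at a scan before cystectomy has little purpose unless progression could otherwise be scored there. The text does not settle the question.

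**Step 3. The plan's own figure.** Section 9.2 gives n = 24, one-sided alpha 0.10, and 90% power for a rise of 27 points from 30%, that is, to 57%. An exact binomial rule requiring at least 11 of 24 event-free gives

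- P(X ≥ 11 | n = 24, p = 0.30) = 0.074
- P(X ≥ 11 | n = 24, p = 0.57) = 0.904

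So the stated 90% reproduces on a binomial basis. The planned test is a log-rank comparison, which cannot be reproduced because the size of the historic subset is not given.

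**Step 4. Weight of one patient.** One patient scored differently at two years moves the rate by 1/27 = 3.7 points (full enrolment) or 1/24 = 4.2 points (the powered sample).

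**Step 5. Sensitivity.** Let k be the number of 24 patients with growth only who, at two years, are event-free under 2.4.1 and events under 6.1.6. The documents do not give k; the values below are assumptions.

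| k | p = 0.30 + k/24 | P(X ≥ 11) | p = 0.57 − k/24 | P(X ≥ 11) |
|---|---|---|---|---|
| 0 | 0.300 | 0.07 | 0.570 | 0.90 |
| 1 | 0.342 | 0.16 | 0.528 | 0.81 |
| 2 | 0.383 | 0.29 | 0.487 | 0.68 |
| 3 | 0.425 | 0.45 | 0.445 | 0.53 |

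Columns 2 and 3 take the rate as 30% under 6.1.6 and score by 2.4.1. Columns 4 and 5 take it as 57% under 2.4.1 and score by 6.1.6.

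**Step 6. Ceiling on k.** Non-completion is 27 × 0.10 = 2.7 patients at the 90% target and 27 × 0.40 = 10.8 at the 60% bound. These are upper bounds at those two rates: the primary endpoint in 2.3.1 is also missed by a cystectomy after sixteen weeks, by fewer than three PULSAR treatments, or by stopping ICI.

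**The case against.** The best defence is that the group affected is small. New lesions and positive pathology are events on both lists. Section 1.4 says that patients found unresectable are managed without curative intent, and where that means starting treatment because of progression, item 3 is met on both lists. The examples of unresectability in 1.4 are distant metastases, which are a new site, and high surgical risk, which is not progression. Enlarging pelvic nodes alone do not rule out cystectomy. All of this stands and limits the number of patients. It does not remove the conflict: item 3 requires treatment to be started, these patients are already on ICI, and 5.5.4 allows study treatment to continue after progression at the investigator's discretion.

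One could also read locoregional recurrence in 2.4.1 as covering growth. That is strained. Disease never removed is persistent rather than recurrent, and item 4 would not need its own growth rule for R2 patients if item 1 already covered growth.

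A reader might infer several stronger points that the documents do not support:

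- *That any scan showing nodal growth is progression under 6.1.6.* It is not at the initial restaging scan, which by the table in 5.4 is the only scheduled post-baseline scan for a patient who never has cystectomy. Nodal growth could count only on later, unscheduled imaging.
- *That an unresected patient has no event under 2.4.1 unless treatment changes.* Items 1 and 2 give other routes.
- *That no reference scan exists for unresected disease.* Section 6.1.3 sets a baseline within 60 days before treatment, 6.1.4.1 uses the nadir, and the non-target rule in 6.1.4.2 does not need measurable lesions.
- *That PFS is inflated by a definite large amount, such as 14 to 20 points.* That would treat every non-completer as unresected at the 60% bound, and would assume without a source that a third to a half of them are misclassified.

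**Conclusion.** The concern holds in a limited form. The two definitions conflict on growth of existing, never-resected disease, and nothing in the plan says which prevails. The conflict is clear for the bladder tumour, and for pelvic nodes on scans after the initial restaging scan, provided that 6.1.6 applies to patients without cystectomy. The scope sentence of 6.1 leaves that uncertain.

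The effect is 3.7 to 4.2 points of 2-year PFS for each patient affected, in the trial's favour under 2.4.1. The total cannot be stated, because k is unknown and a patient counts only if no other event occurs within two years. On the binomial approximation, one such patient would already lift the chance of a positive result at a true 30% from 0.07 to 0.16, above the planned 0.10. This is a secondary endpoint and the primary endpoint is untouched, but a formal test rests on it, so the definitions should be reconciled before analysis.

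**What to change.** Keep one definition. Replace the list in 2.4.1 with a reference to 6.1.6, and have 9.3 cite 6.1.6 by number. Amend the scope sentence of 6.1 so that RECIST progression also applies to patients who do not undergo cystectomy, judged by the nadir reference in 6.1.4.1 and the non-target rule in 6.1.4.2. Keep the 6.1.2 exemption of pelvic nodes at the initial post-PULSAR scan. Where patient-level data allow, score the historic cohort by the same definition; the protocol does not say how progression was defined there.

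Two additions that may suggest themselves are better left out. Resetting the baseline to the pre-surgery scan would contradict the nadir rule and erase earlier bladder growth, although 6.1.2 exempts only pelvic nodes at that scan. Counting the date on which disease is declared unresectable would add an event found in neither list.

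The protocol change is wording only and needs no new scans or patients; re-scoring the historic cohort takes some chart work. The downside is that reported 2-year PFS in all enrolled patients may be somewhat lower. Growth after the pre-surgery scan in unresected patients will still be seen only if imaging is done in routine care.
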